13.3 Method of obtaining informed consent

Before recruitment, each subject will be informed of the nature and purpose of the clinical investigation, procedures, duration and risks and benefits.

The Investigator will inform the subject that participation in the study is completely voluntary and that in no way would refusal jeopardize future treatment or relationships with his doctor.

Furthermore, withdrawal from study is possible at any time without the need for any explanation.

An information sheet written in non-technical language and containing all the most important aspects of the study will be given to the subject and he will be given the opportunity to ask questions to clarify any doubts.

The patient must be given adequate time to reflect before signing the informed consent.

Before any study procedure, the subject will express his or her written consent in a specific document approved by the Ethics Committee.

The informed consent to the study, signed in the original, must be archived by the Investigator after having delivered a copy to the patient.

Any modification to the informed consent must be approved by the Ethics Committee.

The informed consent process will be documented in *the source documents*.

13.4 Participant confidentiality

It is the Investigator's responsibility to ensure that the confidentiality of all subjects participating in the study and all their medical information is maintained throughout the study.

The subjects will be identified by a unique alphanumeric code which will be used in CR and in any other study document. The identifying information will be kept separate in a secure location with access limited to study personnel.

The personnel authorized by the Promoter, or the Ethics Committee or the Regulatory Authority who will have direct access to the study documentation and medical records of the participating subjects for verification purposes, will be bound by the obligation of confidentiality.

13.5 Data processing

Written authorization for the same amount of personal data will be obtained from each subject before recruitment into the study in accordance with EU Regulation 2016/679 and the applicable privacy regulations. Failure to sign the consent to data processing will preclude the possibility of participating in the study.

13.6 Deviations from the clinical investigation plan

The investigator must not deviate from the protocol unless necessary to eliminate an immediate danger to patients in the study.

Any deviation from the clinical protocol will be grounds for exclusion of patients from the study.

Any deviations from the study protocol must be notified to the Sponsor, documented on the appropriate form and communicated to the Ethics Committee, if required by local regulations.

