Endpoints:	
Primary endpoint: Equivalence between the detection of parameters useful for the diagnosis of OSA using the SOUNDI system and standard polysomnographic methods.
 
Secondary endpoints:
 
 • evaluation of satisfaction with the use of SOUND I after the night of recording the parameters, by completing a questionnaire. • safety and tolerability of the SOUNDI device using it recording of adverse events.
Estimated enrollment:	50 subjects
Study population:	Adult subjects belonging to the clinical centre, to carry out a polysomnography for suspicion of a breathing disorder sleep.
Inclusion criteria and exclusion:	
Inclusion criteria:
 
 • Signature of informed consent • Patients of both sexes, of any ethnicity • Age between 20 and 70 years • Prescription, from clinical practice, to carry out a polysomnography on suspicion of a breathing disorder in sleep. 
Exclusion criteria:
 
 • Women during pregnancy • Insufficient cooperation/degree of collaboration in following the procedures required by the study • Participation in another clinical study. • Allergy to one of the materials in the device • Pacemaker users.
Procedures:	
Some data will be collected during a visit anthropometric devices will be positioned simultaneously for polysomnography:
 
 - a traditional polysomnigraph, as prescribed - the experimental Soundi device. 
During the night, at the patient's home, the following parameters will be acquired for at least 8 consecutive hours: oro-nasal flow, thoracic and abdominal respirogram, snoring, ECG, arterial oxygen saturation, body position.
 
The following morning the subject will return to the clinics to return the two systems and complete a simple satisfaction questionnaire prepared for the study.

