3.3 Risks and benefits

The main risks associated with the use of the SOUNDI device by the subjects included in the clinical investigation are:

- Discomfort associated with positioning/removing the measurement unit using double-sided adhesive medical
- Allergic reaction to double-sided adhesive components

These risks will be minimized by the training of the personnel who will place and remove the device from the subject and by the exclusion from the study of subjects with a known allergy to the components of the double-sided adhesive.

The intrinsic risks most related to the design of the device (explosion/fire of the battery, electrocution linked to electrical leakage, emission of electromagnetic radiation, etc.) were evaluated and minimized in the design phase and verified through laboratory tests (electrical safety and electromagnetic compatibility).

The simultaneous collection of vital signs may allow for an early diagnosis of OSA in subjects suspected of having a sleep disorder.

Furthermore, the clinical validation of the SOUND I device on patients will allow the marketing of a small, handy and inexpensive device for the continuous monitoring of vital parameters, capable of collecting useful information for the early diagnosis or follow-up of breathing disorders in sleep.

4. Study design

This is a pre-marketing, single-center, prospective clinical investigation to compare the effectiveness and safety of the SOUNDI medical device compared to polysomnography in detecting parameters for the diagnosis of OSA in subjects suspected of having a sleep disorder.

The study expects to enroll 50 patients.

All patients belong to the Sleep Medicine Center of the Italian Auxological Institute IRCCS-San Luca Hospital in Milan.

After signing the informed consent, the Sound device will be placed in all eligible subjects and at the same time as a traditional polysomnography device the activation of the devices for the acquisition of the parameters will be programmed so that it begins when the subject lies down.

The signals will be acquired for approximately 8 hours during a single night with both systems simultaneously and will then be calculated, via automatic analysis software, with subsequent manual correction by a doctor expert in sleep medicine, the indices used, according to international guidelines, for the diagnosis of breathing and sleep disorders.

No further follow-up is planned for subjects.

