6.3 Exclusion criteria

- Women during pregnancy
- Insufficient cooperation/degree of collaboration in following the procedures required by the study
- Participation in another clinical study.
- Allergy to one of the materials in the device
- Pacemaker users.

7. Study procedures

All subjects enrolled in the study will undergo polysomnography (monitoring

nocturnal cardiorespiratory for the diagnosis of apnea in sleep) with traditional polysomnography (Embletta, Natus) according to normal clinical practice and at the same time as data acquisition with the Soundi system.

On the afternoon before the night of the evaluation, at the Sleep Medicine Service clinic, each object will be placed

- a traditional polysomnigraph, as prescribed
- the Soundi experimental device.

The patient will be instructed by the Investigator on the correct management of the devices.

During the visit, the following anthropometric data will be collected: age, Body Mass Index (BMI), neck circumference and abdomen.

Furthermore, the Experimenter will program the devices to begin recording the parameters at the moment the subject expects to recharge and continue for at least 8 consecutive hours.

During the night, at the patient's home, the following parameters will be acquired with two systems: oro-nasal flow, thoracic and abdominal respirations, snoring, ECG, arterial oxygen saturation (SaO₂), body position.

The following morning the subject will return to the clinics to return the two systems which will be detached by the medical staff. There, the subject will be asked to fill out a simple satisfaction questionnaire prepared for the study.

The signals acquired with both systems simultaneously will be processed by the software RemLogic, via automatic analysis software, with subsequent manual correction by a doctor expert in sleep medicine, the following indices used, according to international guidelines, for the diagnosis of respiratory and sleep disorders:

- Apnea Hypopnea Index (AHI) total and supine
- AHI central
- AHI obstructive
- Oxygen Desaturation Index (ODI)
- Average arterial oxygen saturation (SaO₂).
- Minimum SaO₂
- Time with SaO₂ < 90%
- Average heart rate
- Minimum heart rate
- Percentages of time spent in different body positions.

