7.1 Compliance with procedures

All tests without artifacts invalidating the interpretation of one or more signals acquired for at least 4 hours of sleep will be considered valid.

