8.1 Interruption and withdrawal of subjects from the clinical investigation

Each patient is free to withdraw from the study at any time or his participation may be interrupted by decision of the trial for safety, behavioral or reasons administrative.

Reasons for discontinuing a patient's participation in the study may include:

- withdrawal of consent by the patient
- the change in the patient's clinical-functional conditions that do not allow participation
- lack of adherence to the procedures required by the study protocol on the part of the patient
- an adverse event (related or unrelated to the study device) which, in the opinion of the Principal Investigator, does not allow the continuation of the study itself.

If the study is interrupted for any of the reasons listed above, the measurements taken will not be considered in the statistical analysis.

The reasons for stopping the study will be recorded in CRF.

Unless particular problems are reported to the patient (adverse events or effects related to the use of the device in the study) which will be followed by specific assessments, a follow-up will not be necessary.

Patients excluded from the study and who cannot obtain the data required by the study protocol will be replaced to reach the required number.

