11.3 Analysis set

Efficacy analyzes will be carried out on all patients who have completed the evaluation and whose data will be considered evaluable.

The following will be excluded from the statistical evaluation:

- all measurements lasting less than 4 ha cause the malfunction/
- malposition of the device
- data obtained from measurements of patients excluded from the study.

The safety analyzes will be carried out on all patients to whom the Soundi device and the polysomnography device (safety population) have been applied, regardless of the validity of the data collected.

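### Section 13.6 makes any protocol deviation grounds for exclusion, and 11.3 then drops that patient's data, so a recording valid under 7.1 can leave the primary agreement analysis for reasons unrelated to signal quality

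*Protocol*

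**What the plan says.** - **Protocol 13.6** (deviations): "Any deviation from the clinical protocol will be grounds for exclusion of patients from the study". It does not separate major from minor deviations or patient from staff deviations, and it names neither a decision-maker nor a time point. Deviations are documented and notified to the sponsor.
- **Protocol 11.3** (analysis set): the effectiveness analysis leaves out "data obtained from measurements of patients excluded from the study". Its own duration rule removes only measurements shorter than 4 hours, linked to malfunction or malposition.
- **Protocol 8.1** (interruption and withdrawal): non-adherence and adverse events are among the reasons for stopping a patient. For any of the listed reasons, "the measurements taken will not be considered in the statistical analysis". Patients who are excluded and for whom the required data cannot be obtained "will be replaced to reach the required number".
- **Protocol 7.1** (compliance with procedures): tests free of invalidating artifacts and "acquired for at least 4 hours of sleep will be considered valid".
- **Recording length elsewhere.** Synopsis, procedures: "the following parameters will be acquired for at least 8 consecutive hours". Section 4: "The signals will be acquired for approximately 8 hours during a single night". Section 7 tells the experimenter to program the devices to start at bedtime and "continue for at least 8 consecutive hours".
- **Access to results.** Section 17 has a steering committee of sponsor and principal-investigator representatives regularly review all endpoints as tests accrue. The blinding in 11.4 covers the operator who corrects the scoring manually.

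**The concern.** The protocol has a sensible validity rule in 7.1, echoed by the duration rule in 11.3. Sections 13.6 and 8.1 add further ways out of the analysis that do not depend on whether the recording is usable. If the wording of 13.6 is mandatory, it conflicts with 7.1 for any patient who has a clean recording and some deviation. If it is discretionary, it permits selective exclusion.

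The stake is who enters the only primary analysis of a pre-marketing validation in 50 patients. With a sample of that size, dropping a handful of discordant pairs moves the CCC and the chance of declaring agreement. The estimate would also describe patients who followed every procedure rather than everyone with suspected sleep-disordered breathing and a usable night.

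**Working it through.** **1. The passages applied to one patient.** Suppose both systems yield clean signals for 5 hours of sleep.

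| Rule | Outcome |
|---|---|
| 7.1: at least 4 hours without invalidating artifacts | valid |
| 11.3 duration rule: under 4 hours | not removed |
| Synopsis: at least 8 consecutive hours acquired | falls short, so a deviation on a literal reading |
| Section 4: approximately 8 hours | 5 hours is hard to call approximately 8; 7.5 hours is not |
| 13.6: any deviation | grounds for exclusion |
| 11.3: data of excluded patients | removed |

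No sentence ranks 7.1 against 13.6. The conflict is not confined to short nights: any other deviation in a patient with a clean 8-hour recording has the same result.

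**2. The plan's own sample size.** Inputs from the sample-size paragraph under 11.2: CCC 0.60 under H0, 0.81 under H1, 5% significance (read as one-tailed), 90% power, 50 analysable patients.

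- atanh(0.81) − atanh(0.60) = 1.1270 − 0.6931 = 0.4339
- ((1.645 + 1.282) / 0.4339)² = 45.5
- Adding 2 or 3 (two common variance forms for the transformed coefficient) gives n = 48 or 49, close to the stated 50.
- Power at n = 50: Φ(0.4339·√48 − 1.645) = 91.3%, or Φ(0.4339·√47 − 1.645) = 90.8%.

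The sample size is not at fault.

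**3. What selective exclusion could do.** The documents give no deviation rate, so 10%, 20% and 30% are assumptions. Set-up: 40,000 simulated trials per setting, 50 pairs, bivariate normal, equal means and variances, true CCC 0.60. The test is Z = (atanh(CCC) − atanh(0.60))·√(m − 3) against 1.645, with m the number analysed. A fixed share are deviators, unrelated to agreement. The k deviators with the largest absolute difference are dropped, with or without replacement by new random patients.

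| Deviators among 50 | k = 2 (replaced / not) | k = 3 | k = 5 |
|---|---|---|---|
| none dropped | 4.1% | 4.1% | 4.1% |
| 5 (10%) | 5.6 / 5.7% | 5.4 / 5.5% | 4.2 / 4.3% |
| 10 (20%) | 7.6 / 7.9% | 8.4 / 8.4% | 8.3 / 8.1% |
| 15 (30%) | 9.2 / 9.5% | 10.7 / 11.1% | 11.7 / 12.5% |

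With 5 deviators, k = 5 drops all of them, so nothing is selected and the error stays at baseline. If the number of deviators varies at random around 10%, that cell is about 5%. The mean CCC rises from 0.587 with no exclusions to at most 0.637 in the table. Replacement hardly matters; the inflation comes from choosing whom to drop.

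**The case against.** **Section 7 does not set a minimum for the patient.** Its 8-hour phrase instructs staff how to program the devices. A patient who gets up after 6 hours has not breached that sentence. This stands, and the conflict rests on the synopsis instead, softened by the approximate figure in section 4.

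**Section 7.1 is the specific rule.** It sits under the compliance heading, and 11.3 repeats the 4-hour limit. Many readers would let it prevail over a general administrative sentence. That is reasonable, but 13.6 covers any deviation and 11.3 drops every excluded patient without reference to 7.1, so the text does not settle it.

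**Exclusion after the results are known.** A reader might infer this. The protocol does not say so, deviations and reasons for stopping must be recorded, and the scorer is blinded. The supportable statement is narrower: nothing prevents it, because the committee in section 17 sees endpoints as they accrue and the stated blinding does not extend to whoever decides exclusions. A SAP could set the timing. It would still inherit the two conflicting rules.

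**Automatic replacement.** A reader might infer that a patient with a valid short night would be replaced. Section 8.1 adds the condition that the required data cannot be obtained, so this is open to interpretation. The bias does not depend on it.

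**The 8.1 limb is small.** Participation lasts at most 24 hours with one recording night, so few patients would stop after a usable recording exists. This stands.

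**Size.** Dropping the most discordant of all 50 patients would give roughly 16% and 23% for k = 2 and 3, and 36–41% for k = 5. That needs a deviation in every discordant patient, which the protocol gives no reason to expect. The documents also do not show that short nights agree worse. Finally, agreement is assessed for each of about ten indices; selection on one would leave an independent index at about 4%, and correlated indices fall in between.

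**Conclusion.** The point holds as a defect of stated rules, not as missing detail. Sections 13.6 and 11.3, and to a lesser degree 8.1, let a recording that meets 7.1 leave the primary analysis for reasons unrelated to its quality, and the protocol does not say which rule governs. It should be fixed, but it does not by itself invalidate the design.

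The textual conflict is certain for deviations in general. For short nights it depends on reading the synopsis figure literally. The size is illustrative: under assumed deviation shares of 10% to 30% and worst-case choice on a single index, false success moves from about 4% to between 5% and 13%. If exclusions are made without regard to agreement, there is no such inflation and the cost is lost patients: without replacement, power would be about 88% at 45 analysed.

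**What to change.** - **13.6:** replace the exclusion sentence. Deviations are documented and reported, but a patient's data leave the effectiveness analysis only if consent to their use is withdrawn, an eligibility criterion was not met, or the recording fails the 7.1/11.3 validity rule, including malposition or malfunction as described in 11.4. The decision is made and dated before the SOUNDI and polysomnograph indices are compared.
- **8.1 and 11.3:** state that recordings already meeting 7.1 are kept when participation stops for non-adherence or an adverse event, and that a recording shorter than 8 hours which meets 7.1 is not in itself a reason for exclusion. Align the recording-length wording in the synopsis and sections 4 and 7 with this.
- **8.1, replacement:** make explicit that it applies only to patients without a valid recording.

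The cost is protocol wording. No patients or procedures are added, N = 50 keeps its stated power, and fewer replacements may be needed. The downside is that agreement may look slightly less favourable.

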13.7 Study monitoring

Monitoring of the study will be carried out by the Promoter's staff.

Monitoring activities will be carried out periodically at the center, according to the monitoring plan.

The aim of the monitoring is to verify that the rights and well-being of patients are protected, that the study data reported is accurate, complete and verifiable on the basis of the original data and that

the study is conducted in accordance with the protocol, the study procedures, the ICH-GC and the requirements regulatory.

The Investigator must give the monitors direct access to the original study documents (provided that the confidentiality of the subjects is protected) and provide adequate space and time to carry out monitoring.

13.8 AuditedInspections

To ensure compliance with the protocol, study procedures, ICH-GCP and all applicable regulatory requirements, the Sponsor may conduct an audit at the participating centre.

The Regulatory Authority may carry out an inspection of the study. The Principal Investigator must promptly inform the Sponsor if an inspection by the Regulatory Authority has been scheduled at his site.

Such audits/inspections may be carried out at any time during or after the completion of the study.

In the event of an audit, the Principal Investigator and the Institution agree to allow the auditor/inspector direct access to all relevant documents and to ensure that time is available to discuss the results of the audit/inspection and any findings in the presence of the Sponsor, if required or necessary.

14. Ownership and Data Publication Policy

The Promoter is the exclusive owner of all information arising from the clinical investigation, including resulting data, results, discoveries, inventions, know-how and similar.

The results deriving from the clinical investigation may be the subject of joint publication in the name of the Promoter and the Principal Investigator. These results may be published in national and international journals or presented at similar congresses, conferences, seminars.

15. Data management and storage

15.1 Sourcedocuments

The Investigator must keep adequate and accurate documentation to allow the execution of the study to be fully documented and to subsequently verify the clinical investigation data.

Source documents are generally the documents on which information or data were recorded for the first time and may include patient medical records, questionnaires, as well as diagnostic test results.

The Investigator is responsible for ensuring the reliability, accuracy, completeness, originality and readability of the data reported in the source documents.

If requested, the Investigator will provide the Sponsor and the Regulatory Authority with direct access to the source documents.

15.2 CaseReportForm

An electronic Case Report Form (eCRF) will be used in this study to meet regulatory requirements, ensuring system validation, traceability and audit trail, preservation, protection, reproducibility and recovery of experimental data, control of access to information and electronic signature.

Center staff will receive training in accessing the eCRF and entering data. Only designated and trained staff will receive personal access to the eCRF.

The data reported in the eCRF must be consistent with the source documents. The eCRF will never be considered as a source document for the study.

15.3 Document storage

The Investigator will have to keep the documentation relating to this clinical investigation for at least 10 years from the conclusion or for a longer period, if required by the applicable legislation.

The documentation of the clinical investigation must be kept in a safe place which, if necessary, allows for timely recovery.

If the Investigator wishes to transfer the clinical investigation documents to another location, he/she must inform the Sponsor in advance.

16. Insurance

The insurance coverage of the risks relating to the study is guaranteed by an insurance policy stipulated ad hoc by the Promoter pursuant to the Ministerial Decree of 14 July 2009. The insurance coverage will be covered by the Promoter.

17. Steering Committee

This study will have a data monitoring steering committee which will include representatives of the Promoter and the Principal Investigator. All study endpoints, objectives and safety data will be reviewed regularly by the steering committee which will meet periodically in order to carry out a timely analysis of the tests progressively carried out. The steering committee will have the possibility to decide to suspend the investigation in case of security problems and may

recommend changes to the investigation, including discontinuation, if there is a change in the risk/benefit ratio for participating subjects.

18.Bibliography

[1]PhysiologicalMonitoringDevice

<https://worldwide.espacenet.com/patent/search/family/056940255/publication/EP3248541B1?q=pn%3DEP3248541B1>

[2]Marzorati,D.,Bovio,D.,Salito,C.,Mainardi,L.,&Cerveri,P.

(2020).ChestwearableapparatusforcufflesscontinuousbloodpressuremeasurementsbasedonPPGandPCGsignals. *IEEEAccess*, 8, 55424-55433.

[3]Marzorati,D.,Dorizza,A.,Bovio,D.,Salito,C.,Mainardi,L., &Cerveri,P.(2022).HybridConvolutionalNetworksforEnd-to-EndEventDetectioninConcurrentPPGandPCGSignalsAffectedbyMotionArtifacts.

IEEE Transactions on Bio-medical Engineering.

[4]Rossi,M.,Alessandrelli,G.,Dombrovski,A.,Bovio,D.,Salito,C.,Mainardi,L.,&Cerveri,P.(2022).IdentificationofCharacteristicPointsinMultivariatePhysiologicalSignalsbySensorFusionandMulti-TaskDeepNetworks. *Sensors*,22(7),2684.

[5]RossiM.,SalaD.,BovioD.,SalitoC.,AlessandrelliG.,LombardC.,MainardiL.,CerveriP.(2022) SLEEP-SEE-THROUGH:explainabledeeplearningforsleepeventdetectionandquantificationfromwearablesomnography. *SubmittedtoIEEEJournalofBiomedicalandHealthInformatics*.

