8.2 Early closing or suspension of the study

The Promoter reserves the right to interrupt or suspend the study at any time for reasonable medical, safety, or administrative reasons.

The Sponsor will notify the Ethics Committee and the Principal Investigator of the decision to suspend or interrupt the study with the reasons. It will also provide the trial with specific instructions to inform the patients and indications on the procedures to be followed.

Circumstances that may justify interruption or suspension of the study:

- Determination of an unexpected, significant or unacceptable risk to participants
- Any serious or persistent case of non-compliance with the legislation
- Suspension or termination of Ethics Committee approval
- The feedback from the data is excessively different from that expected.

In the event of suspension, the study may be resumed once issues of safety, protocol compliance or data quality have been resolved to the satisfaction of the Sponsor and the Ethics Committee.

9. Evaluation of effectiveness

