9.1 Primary endpoint

The primary endpoint of the study is the equivalence between the detection of parameters useful for the diagnosis of OSA using the SOUNDIV system and standard polysomnographic methods.

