11.1 Effectiveness analysis

The continuous variables will be reported as the mean value and standard deviation or as the median and interquartile range in the case of non-normally distributed data. Therefore, for each parameter the agreement between the measurement carried out with the SOUNDI method and the one carried out with polysomnography (gold standard) will be evaluated using the Bland-Altman graph and the Concordance Correlation Coefficient (CCC) [6]. In short, this graph represents the value of the differences of the measurements carried out with two methods differ from their average[7]. The CCC varies between -1 and 1, values between 0.61 and 0.80 indicate substantial agreement while values greater than 0.81 almost perfect agreement according to the Landis and Koch scale [8].

Descriptive statistics will be used to evaluate the subject's satisfaction with using SOUNDI.

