11.2 Securityanalysis

The safety analyzes will be carried out on all patients to whom the Sound device and the polysomnography device have been applied, regardless of the validity of the data collected.

In general, safety analyzes will be descriptive in nature. The frequency, severity, severity and causal relationship of adverse events will be tabulated.

Both the number and percentage of events and patients experiencing an event will be presented. Additionally, adverse events that led to study suspension and device defects reported.

Sample size.

A sample of 50 analyzable patients will guarantee a power of 90% in determining six values of the parameters detected with the SOUND I method are in agreement with those measured by polysomnography. The estimate was made considering: i) a z-head and a tail with a significance level of 5%; ii) a value of the CCCparia 0.60 below H0; iii) a value of the CCCparia 0.81 below H1 . Sample sizing was performed using PASS2021(PowerAnalysisandSampleSizeSoftware(2021).NCSS,LLC.Kaysville,Utah,USA).

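### Section 17 opens SOUNDI–polysomnography agreement to the sponsor and investigator as tests accrue, while exclusions are still open, and section 8.2 does not rule out stopping on it

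*Protocol*

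**What the plan says.** Section 17 sets up a data monitoring steering committee that includes representatives of the sponsor and the Principal Investigator. "All study endpoints, objectives and safety data will be reviewed regularly by the steering committee which will meet periodically", and the purpose is given as "in order to carry out a timely analysis of the tests progressively carried out". Endpoints are named separately from safety data. The committee may suspend the study for safety problems, and it may "recommend changes to the investigation, including discontinuation, if there is a change in the risk/benefit ratio for participating subjects".

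Section 9.1 states: "The primary endpoint of the study is the equivalence between the detection of parameters useful for the diagnosis of OSA". Section 11.1 assesses this by Bland-Altman plot and CCC for each parameter, and notes that "values between 0.61 and 0.80 indicate substantial agreement".

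Section 8.2 lets the sponsor interrupt or suspend the study for reasonable medical, safety or administrative causes. Among the circumstances that may justify this it lists "The feedback from the data is excessively different from that expected". After a suspension, "the study may be resumed once issues of safety, protocol compliance or data quality have been resolved".

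The sample-size paragraph, under section 11.2, states: "A sample of 50 analyzable patients will guarantee a power of 90" per cent, for a one-tailed 5% test of CCC 0.60 against 0.81. It mentions no interim look.

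**The concern.** The protocol itself puts the primary comparison within a recurring review by the people who run and fund the study. Nothing in it keeps agreement results out of that review or out of the 8.2 ground for stopping. Two things follow.

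**Exclusions made with agreement in view.** Several decisions about who counts are matters of judgement:
- whether data are evaluable (11.3);
- whether bad positioning makes a signal incomparable with polysomnography (11.4);
- whether a protocol deviation leads to exclusion (13.6);
- replacement of excluded patients (8.1).

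The blinding in 11.4 covers only the expert who corrects the scoring. It does not cover the sponsor or the investigator in their committee role. If discordant pairs were more readily judged unusable, the final CCC would be biased upwards.

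**A stop on low agreement.** If early agreement looked poor and this was treated as an 8.2 ground, some studies of a device that meets the planned CCC of 0.81 would end early by chance. The stated power would then no longer hold.

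**Working it through.** **1. The plan's own figure.** Inputs from the sample-size paragraph: null CCC 0.60, alternative 0.81, one-sided 5%, power 90%.

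- Fisher z: atanh(0.81) − atanh(0.60) = 1.1270 − 0.6931 = 0.4339.
- n = ((1.645 + 1.282)/0.4339)² + k = 45.5 + k. This gives 47.5, so 48 patients, with variance 1/(n−2), or 48.5, so 49 patients, with variance 1/(n−3).
- Power at n = 50, variance 1/(n−3): Φ(√47 × 0.4339 − 1.645) = Φ(1.33) = 0.908. With 1/(n−2) it is 0.913.

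The stated 50 patients and 90% are therefore right for a single final analysis.

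**2. Looking without acting.** If the committee sees agreement and nothing is done, the test at n = 50 is the same test. Power and type I error do not change.

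**3. Stopping on low agreement.** The protocol gives no looks and no cut, so both are assumed. Cuts end at 0.60 because 11.1 calls the range above that substantial agreement. The simulation uses bivariate normal pairs with equal means and variances, for one parameter. The final test at n = 50 uses variance 1/(n−3), so the critical CCC is tanh(0.6931 + 1.645/√47) = 0.732. The study stops if the observed CCC falls below the cut. With no stop, power is 90.2% and type I error 4.2%.

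Power (%) at true CCC 0.81:

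| Looks at n | Cut 0.40 | Cut 0.50 | Cut 0.60 |
|---|---|---|---|
| 25 | 90.2 | 90.1 | 89.4 |
| 20, 35 | 90.1 | 89.9 | 88.3 |
| 20, 30, 40 | 90.2 | 90.0 | 88.3 |
| 10 only | 88.4 | 86.2 | 80.9 |
| 10, 20, 30, 40 | 88.4 | 86.0 | 80.3 |

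The first two rows come from 400,000 runs and the last three from a separate 300,000. Differences of 0.1–0.2 points are simulation noise.

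- First look at 20 or later: the largest loss is 90.2 − 88.3 = 1.9 points.
- A look at 10: the loss runs from 90.2 − 88.4 = 1.8 to 90.2 − 80.3 = 9.9 points.
- The single look at 10 accounts for nearly all of the loss with four looks, and three looks from 20 onwards cost no more than two. What drives the loss is how early the first look comes, not how many looks there are.
- Chance of a false stop at true CCC 0.81, for cuts 0.40/0.50/0.60: 0.1/0.4/2.2% with one look at 25, and 2.9/6.3/14.1% with looks every 10 patients.
- At true CCC 0.85, power is 98.5% with no stop and stays at 92% or more under one look at 25, looks at 20 and 35, and looks every 10.
- At true CCC 0.60, type I error under those same three schedules is 3.3–4.2%. A stop for poor agreement can only remove rejections, so it cannot inflate this error.

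**4. Exclusions with agreement in view.** The protocol gives no figure for how many recordings turn on judgement, so this part cannot be sized.

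**The case against.** **No stated rule produces the harm.** The loss of power requires that the committee computes a CCC, that the sponsor treats a low value as an 8.2 ground, and that it does so at particular looks and cuts. The protocol states none of these, and a statistical analysis plan or charter that is not shown may settle them. This stands, and it is why the exposure is conditional. It does not remove the point, because section 17 itself states that all endpoints are reviewed as tests accrue.

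**Section 8.2 is not open-ended.** Its governing sentence requires a reasonable medical, safety or administrative cause. That narrows the data ground, but administrative is a broad word and agreement is not excluded. The clause on resuming applies only after a suspension, so it does not define when the study may be stopped.

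**Reviewing endpoints fits the committee's remit.** Section 3.3 counts earlier diagnosis and clinical validation among the benefits, so performance can bear on risk/benefit. Recordings also have to be checked for validity as they arrive (7.1, 8.1). Both points are fair. A reader might infer that section 17 contradicts itself by giving the committee endpoints but powers over safety and risk/benefit only; the text does not support so strong a contrast. The protocol also does not say that a CCC is calculated at each meeting.

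**The stronger reading is inflated type I error.** A reader might infer that repeated looks raise the false-positive rate. That would need a favourable look to end the study with success declared on the unadjusted test; simulated type I error would then be about 7–13% for 2–10 looks. The protocol provides for no early success stop, so this reading is not supported.

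**Conclusion.** The point holds as a conditional exposure. It is not an error in a stated figure or a contradiction. Section 17 includes agreement in the ongoing review, section 8.2 leaves a data ground undefined, and no other section separates agreement from either.

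The firmer part is that the sponsor and investigator may see accruing agreement while judgement-based exclusions and replacements are open. The protocol does not show that this would be misused, and the effect cannot be sized from it.

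The second part is a loss of power at CCC 0.81, and only if agreement drove a stop: about 0–2 points with a first look at 20 or later, about 2–10 points with a look at 10. These ranges rest on assumed looks, on cuts of 0.40–0.60, on bivariate normal data without bias between devices, and on a single parameter. A reader might take the 10-point figure as the expected loss. It is the extreme of the assumed rules and depends on stopping after 10 patients.

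This is a cheap improvement worth making, not a flaw that undermines the sample size.

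**What to change.** **Section 17.** Limit periodic review to safety, recruitment and technical validity of recordings. State that no summary agreement statistics (CCC, Bland-Altman) are computed or shown to the committee until the data of the 50th analysable patient are locked.

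**Validity checks.** State that checks of individual recordings continue, including the 11.4 check that a malpositioned signal is comparable with polysomnography, and that they are decided without sight of the differences in the derived indices. That check compares the two devices, so a blanket ban on paired viewing would not work.

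**Section 8.2.** State that the data ground covers safety, device defects and data quality, not agreement results.

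**Cost.** Wording only. The committee keeps its power to suspend for safety and its safety review. The sponsor loses early sight of agreement, and any view of risk/benefit that draws on agreement waits until the data are locked.
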